### 11.3. Reporting to FDA

Serious adverse events will be forwarded to FDA by the IND Sponsor (AROG) according to 21 CFR 312.32.

It is the responsibility of the PI and the research teams to ensure serious adverse events are reported according to the Code of Federal Regulations, Good Clinical Practices, the protocol guidelines, the sponsor's guidelines, and Institutional Review Board policy.

### 12. STATISTICAL CONSIDERATIONS

### 12.1. General Considerations

There will be two parallel arms for the study: one for Crenolanib Combined with standard salvage chemotherapy; the other is for Crenolanib Combined with 5-Azcytadine in Patients with Acute Myeloid Leukemia with Activating FLT3 Mutations. Arm 1 is for the AML or high-risk MDS patients who are refractory or has relapsed after prior therapy. Patients will be treated with standard salvage chemotherapy combined with crenolanib. Arm 2 is for the AML or high-risk MDS with no more than one prior salvage therapy or previously untreated. Patients will receive azacitidine combined with crenolanib. For each arm, there will be a phase I part to identify the MTD of crenolanib combined with either standard salvage chemotherapy or 5-Azcytidine.

Phase I
Table 12.1. Dose levels of Crenolanib (applies to both Arms 1 and 2)

Dose Level	Crenolanib mg PO daily
0	60 mg BID
1 (Starting dose)	60 mg TID

2	80 mg TID
3	100 mg TID

First, phase I study is performed to assess the safety of different dosing regimens. Three combination dose levels are defined; the starting dose is dose 1. Dose levels of crenolanib apply to both arm 1 and 2. A Rolling-6 design will be used to for dose escalation and de-escalation. A maximum of 18 patients will enroll in the phase I study. Patients will be entered sequentially to each dose level. The DLT in phase I is based on the 1st cycle adverse event. If at least 2 of 3 or 2 of up to 6 patients experience a DLT at the starting dose level, then deescalate to the next lower dose. The MTD is defined as the highest dose level in which <2 patients of 6 develop first cycle DLT.

### Phase II

The method of Thall, Simon and Estey [30] will be used for futility and toxicity monitoring for each arm. The 6 patients treated in the phase I MTD dose will be included in the phase II part. The primary endpoint is the response rate (CR+CRi+CRp+PR) after one or two cycles of treatment. The historical data suggested the response rate is 10%. With the assumption that the improved response rate to be 25%, it is estimated that a total of 32 evaluable patients including the 6 patients from phase I will yield 79% power at a significance level of 10% (two-sided) based on chi-square test (nQuery software version 7.0).

The response (CR+CRi+CRp+PR) denoted as RR, and toxicity (grade 3 or 4 non-hematologic toxicity not expected from chemotherapy alone), denoted as TOX, will be monitored simultaneously by Bayesian stopping boundaries calculated based on beta-binomial distribution. Independence is assumed between RR and TOX. There are no historical data available. The current regimen will be considered promising if the RR rate is at least 25% and the TOX rate is below 30%. The prior probabilities of RR and TOX for the regimen are modeled by beta distributions (Beta(0.5, 1.5) and Beta(0.6, 1.4), respectively). Denoting the probabilities of the RR rate and TOX by  $\{\theta_{RR}, \theta_{TOX}\}$ , the following decision criteria will be applied:

- 1) stop if Prob{  $\theta_{RR} < 0.25 \mid data$ } > 0.98, and
- 2) stop if Prob{  $\theta_{TOX} > 0.3 \mid data$ } > 0.85

Patients will be monitored by a cohort size of 4 according to the following stopping boundaries for RR and toxicity. If the number of responses required for moving the trial to next stage has not been achieved, the patient enrollment will be halted until enough responses observed. The design software Multc Lean Desktop (version 2.1) developed by the Department of Biostatistics at MD Anderson Cancer Center (MDACC) was used to generate the futility/toxicity stopping boundaries and the OC table.

**Table 12.2.** Stopping boundaries for response (RR) and toxicity

Number of patients evaluated	Stop the trial if there are this many response	Stop the trial if there are this many unacceptable toxicities
4	Never stop	3-4
8	Never stop	5-8
12	0	6-12

16	0	7-16
20	0-1	9-20
24	0-2	10-24
28	0-2	12-28

The operating characteristics are summarized in the following table.

Table 12.3. Operating characteristics of efficacy and safety monitoring

True Toxicity Rate	True RR Rate	Prob (stop the trial early)
0.1	0.05	0.90
0.1	0.1	0.61
	0.15	0.33
	0.25	0.07
	0.35	0.01
0.2	0.05	0.9
	0.1	0.63
	0.15	0.37
	0.25	0.12
	0.35	0.07
0.3	0.05	0.93
	0.1	0.72
	0.15	0.52
	0.25	0.33
	0.35	0.29
0.4	0.05	0.96
	0.1	0.86
	0.15	0.76
	0.25	0.67
	0.35	0.65

Summary statistics will be provided for continuous variables. Frequency tables will be used to summarize categorical variables. The response (RR) rate will be estimated along with the exact 95% confidence interval.

Data from all subjects who receive any study drug will be included in the safety analyses. Subjects who entered the study and did not take any of the study drugs and had this confirmed will not be evaluated for safety. The severity of the toxicities will be graded according to the NCI CTCAE v4.0 whenever

possible. We will follow standard reporting guidelines for adverse events. Safety data will be summarized by category, severity and frequency. The proportion of patients with AEs will be estimated, along with the Bayesian 95% credible interval.

Any change to the data analysis methods described in the protocol will require an amendment ONLY if it changes a principal feature of the protocol. Any other change to the data analysis methods described in the protocol, and the justification for making the change, will be described in the clinical study report. Additional exploratory analyses of the data will be conducted as deemed appropriate.

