#### 3. STUDY DESIGN

This is a Phase I/II, two arm, open label study in FLT3 mutation positive AML of treatment given as either:

Arm 1: crenolanib with standard salvage chemotherapy

Arm 2: crenolanib with 5-azacitidine

Assignment to treatment arm will be determined by the Investigator with enrollment to each arm to occur simultaneously.

Crenolanib will be administered for the phase 1 portion as described according to dose levels in Table 6.2. Phase I will use a rolling-6 design and plan for a total of 18 patients on each arm. The starting dose will be 60 mg TID (dose level 1). Dose escalations will proceed to 80 mg TID (dose level 2) and 100 mg TID (dose level 3) based on DLTs (as defined in section 6.3). DLTs will be evaluated during the first cycle of crenolanib treatment. Patients who experience crenolanib related DLTs at dose level 1 will receive a dose reduction to dose level 0 (60 mg BID). Patients who encounter DLTs at dose levels 2 and 3 will receive dose reduction at 1 dose level lower.

Phase II total of 26 patients in each arm treated at established phase I dose.

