2	0, 1	Any	Any	Stay	
2	2	0	0	De-escalate	
3	0	0, 1, 2	3, 2, 1	Stay	
3	0	3	0	Escalate	

3	1	0, 1, 2	2, 1, 0	Stay	
3	$\geq 2$	Any	Any	De-escalate	
4	0	0, 1, 2, 3	4, 3, 2, 1	Stay	Stay
4	0	4	0	Escalate	Stay
4	1	0, 1, 2, 3	3, 2, 1, 0	Stay	Stay
4	≥ 2	Any	Any	De-escalate	De-escalate
5	0	0, 1, 2, 3, 4	5, 4, 3, 2, 1	Stay	Stay
5	0	5	0	Escalate	Stay
5	1	0, 1, 2, 3, 4	4, 3, 2, 1, 0	Stay	Stay
5	$\geq 2$	Any	Any	De-escalate	De-escalate
6	0	0, 1, 2, 3, 4	6, 5, 4, 3, 2	Suspend	Suspend
6	0	5, 6	1, 0	Escalate	MTD not determined
6	1	0, 1, 2, 3, 4	5, 4, 3, 2, 1	Suspend	Suspend
6	1	5	0	Escalate	MTD not determined
6	≥ 2	Any	Any	De-escalate	De-escalate

The MTD is empirically defined as the highest dose level at which 6 patients have been treated with at most 1 patient experiencing a crenolanib related DLT and the next higher dose level has been determined to be too toxic. The maximum tolerated dose (MTD) may be further defined based on incidence of delayed or cumulative toxicity.

Approximately 88 patients (a maximum of 18 patients in each arm for determination of MTD and 26 patients each arm for phase II portion) will be enrolled in the study. In the dose finding phase I, a maximum of 6 patients at each dose level will be enrolled to establish the proper dose for phase II. As a result, as few as 6 patients and as many as 18 patients can be enrolled in phase I. The recommended dose of crenolanib for testing in the expansion phase will be tentatively identified in the dose escalation phase and will be that which is at or below the MTD, that can be delivered safely in multiple cycles with an acceptable incidence of on-time delivery, and that confers exposure consistent with that needed for efficacy based on the nonclinical models. Once the proper dose has been determined for phase II, an additional 26 patients will be enrolled in each arm.

Table 5.2. Dose levels of crenolanib (applies to both Arms 1 and 2)

Dose Level	Crenolanib mg PO daily during induction
0	60 mg BID
1 (Starting dose)	60 mg TID
2	80 mg TID
3	100 mg TID

Dose adjustments beyond those mentioned in this table or different to the doses specified may be acceptable after discussion with the PI and notification of the sponsor and documentation of the justification recorded in the chart.

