### 12.4. Determination of sample size

A total of 88 AML patients with FLT3 activating mutation will be enrolled. There are two study arms (44 patients per arm). Patients will receive crenolanib with chemotherapy. Arm 1 is for the AML or high-risk MDS patients who are refractory or has relapsed after prior therapy. Patients will be treated with standard salvage chemotherapy combined with crenolanib. Arm 2 is for the AML or high-risk MDS. Patients will receive azacitidine combined with crenolanib. For each arm, there will be 44 patients: in phase I, with 3 dose levels and Rolling-6 design, a maximum of 18 patients will be needed. With the 6 patients in the MTD dose enrolled in the following phase II part, for each arm, there will be 32 patients in total for phase II. In phase II, the primary endpoint is the response rate (CR+CRi+PR) after one or two cycles of treatment. The historical data suggested the response rate is 10%. With the assumption that the improved response rate to be 25%, it is estimated that a total of 32 evaluable patients

including the 6 patients from phase I will yield 79% power at a significance level of 10% based on chi-square test (nQuery software version 7.0).

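### Phase II pools the six patients treated at the phase I MTD, but the phase II dose may be set below the MTD; pooling should follow the selected dose

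*Combined protocol and SAP*

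**What the plan says.** Section 12.1 (Phase II): "The 6 patients treated in the phase I MTD dose will be included in the phase II part". The primary endpoint is the response rate after one or two cycles, and the sample size is "a total of 32 evaluable patients including the 6 patients from phase I".

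Section 12.4 repeats the rule: "With the 6 patients in the MTD dose enrolled in the following phase II part", giving 32 per arm.

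Section 5.1 chooses the expansion dose on wider grounds than first-cycle DLTs. It "will be that which is at or below the MTD". The choice also weighs whether the dose can be given safely and on schedule over several cycles, and whether exposure is consistent with efficacy in nonclinical models. Then "an additional 26 patients will be enrolled in each arm".

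Section 3: "Phase II total of 26 patients in each arm treated at established phase I dose". The established dose is not defined there as the MTD.

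The six also enter the monitoring. They are counted in phase II, and Table 12.2 has a look at 28 patients, which 26 new patients alone could not reach.

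**The concern.** The pooling rule is tied to the MTD, while the 26 new patients are tied to the selected dose. Section 5.1 expressly lets the selected dose be lower. No section says that the two must be equal, or which phase I patients are pooled if they are not.

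Read literally, a lower selected dose would bring six patients from a higher dose into the primary response estimate and into the response and toxicity boundaries. The reported rates would then not describe the dose taken forward. Table 12.3, which assumes one response rate and one toxicity rate for all patients, would not describe how the trial behaves.

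**Working it through.** **Inputs from the documents.** Six pooled and 26 new patients per arm; historical response rate 10%, target 25%; two-sided 10% chi-square test with 79% power (section 12.1); boundaries in Table 12.2 with looks every 4 patients from 4 to 28. The response and toxicity rates used below for the six patients are assumptions.

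**1. The plan's power.** For a one-sample chi-square test against a fixed 10%, in the normal approximation:

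power = Φ[(p1 − p0 − 1.645·√(p0(1−p0)/n)) / √(p1(1−p1)/n)]

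At n = 32, √(0.10×0.90/32) = 0.0530 and √(0.25×0.75/32) = 0.0765. This gives Φ[(0.15 − 1.645×0.0530)/0.0765] = 79.4%, which reproduces the stated 79%.

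**2. Rejection limit.** At 6/32, z = (0.1875 − 0.10)/0.0530 = 1.65, which just exceeds 1.645. At 5/32, z = 1.06. The test therefore rejects at 6 or more responses. With 10% response in all 32, the exact P(≥6) is 9.4%.

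**3. Share of the primary set.** 6/32 = 18.75%, or 19%.

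**4. Effect on the response test.** The total is Binomial(6, rate in the six) plus Binomial(26, 0.10). The pooled rate is (6 × rate in the six + 26 × 0.10)/32.

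| Assumed response in the six | Pooled rate | P(≥6 of 32) |
|---|---|---|
| 10% (no mixing effect) | 10.0% | 9.4% |
| 15% | 10.9% | 13.0% |
| 20% | 11.9% | 17.1% |
| 25% | 12.8% | 21.7% |

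**5. Effect on monitoring.** All Table 12.2 boundaries follow from the stated beta priors and cut-offs, and all Table 12.3 entries reproduce to within 0.01 by exact recursion with one common rate. With the six counted first:

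- Toxicity 20% throughout and response 10% at the phase II dose: P(stop early) falls from 0.63 to 0.39 if the six respond at 25%. An inactive dose is more likely to continue.
- Response 25% throughout and toxicity 20% at the phase II dose: P(stop early) rises from 0.12 to 0.20 or 0.31 if toxicity in the six is 30% or 40%.

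**6. Where the stopping happens.** Table 12.2 has no response stop at 4 or 8 patients; only toxicity can stop the trial there. With response 10% and toxicity 20% in all patients, those two looks contribute 0.03 of the 0.63. Response stopping starts at 12 patients, where the six are half the data.

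**7. N and power if pooling follows the selected dose.** The formula in step 1 gives 79.4% with six eligible phase I patients (n = 32), 76.6% with three (n = 29) and 73.5% with none (n = 26).

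**8. Whether an MTD group exists.** Under section 5.1 the MTD requires the next higher level to be too toxic, and Table 5.1 records the MTD as not determined when six patients clear the highest level. Section 12.1 defines the MTD as the highest level with fewer than 2 of 6 DLTs, so it would call that same level the MTD. Under the section 5.1 definition there is then no MTD group to pool.

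**The case against.** The best reply is that section 12 uses the MTD dose as shorthand for the phase II dose. Section 5.1 lets the MTD be further defined by delayed or cumulative toxicity, so the multi-cycle tolerability grounds for a lower dose could be absorbed into the MTD itself. Nothing says that a lower dose is expected. This reading is plausible, but it is stated nowhere, and section 5.1 keeps the MTD and the expansion dose apart.

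A second reply concerns size. No dose-response data in the documents support a gap of 25% versus 10%, and the exposure requirement in section 5.1 argues against a null-level response at the selected dose. That stands. The results are illustrations, and the 15% row shows the mild case. The higher-toxicity scenarios are also tempered, because the MTD group is selected for at most 1 of 6 first-cycle DLTs.

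A reader might infer that the first two looks, made up wholly or mostly of these six patients, drive stopping. Table 12.2 does not support this. Only toxicity can stop the trial at 4 and 8 patients, and in the scenario of step 6 those looks supply about 5% of the stopping probability (0.03/0.63).

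**Conclusion.** The mismatch between section 5.1 and sections 12.1 and 12.4 is in the text and should be corrected. Its harm is conditional: it arises only if the selected dose is below the MTD. In that case 19% of the primary set comes from another dose, and Table 12.3 does not apply. With 10% response at the phase II dose, the chance of a positive result would be 13.0% to 21.7% in place of 9.4%, under assumed response rates of 15% to 25% in the six.

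A reader might go further and conclude that the power calculation is wrong or that phase II will certainly mix doses. Neither follows. The 79% reproduces, and it stands unchanged if the selected dose is the MTD.

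**What to change.** - In sections 12.1 and 12.4, define the pooled patients as the phase I patients in that arm who were treated at the selected phase II dose.
- State that the same set is used for the Table 12.2 boundaries.
- State N and power if fewer than six qualify. Table 5.1 permits escalation after three patients without DLT, so a level below the MTD may hold only three: about 77% at n = 29, and about 73% at n = 26 if none qualify.
- Reconcile the MTD definition in section 5.1 and Table 5.1 with that in section 12.1, so that the group to be pooled exists in every outcome of phase I.

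The cost is a sentence in each of two sections, a short statement of N and power, and one reconciled definition. With six eligible patients, power is unchanged; with fewer, the loss is up to about 6 percentage points (79.4% to 73.5%) unless more patients are enrolled. The change selects no dose and alters no clinical rule.

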### Justification for using a higher rate of serious toxicity for the early stopping criteria:

Refractory or relapsed AML remains among the most challenging scenarios in the management of AML due to lack of highly effective and standardized treatments for this situation. These patients are willing to take the risk of receiving an investigation drug to increase their chance of survival compared to average patients. Whenever possible, refractory/relapsed patients should be enrolled in clinical trials. The stopping boundary is set as such to make sure the trial will not get terminated prematurely due to serious toxicities which occurs if the boundary is too low.

### 12.2. Patient Disposition

A a	etailed description of patient disposition, broken by conort, will be provided. It will include:
	Summary of patients entered
	Total number of patients entered
	Total number of patients enrolled
	Summary of reasons for patients entered, but not enrolled
	Summary of reasons for patient discontinuation from study treatment
	Summary of all identified important protocol violations
12.3	3. Patient Characteristics
12.3	B. Patient Characteristics ent characteristics will be reported for each cohort, and include a summary of the following:
12.3	3. Patient Characteristics
12. 3 Pati □	B. Patient Characteristics ent characteristics will be reported for each cohort, and include a summary of the following:
12. 3 Pati □	B. Patient Characteristics ent characteristics will be reported for each cohort, and include a summary of the following: Patient demographics
12.3	B. Patient Characteristics ent characteristics will be reported for each cohort, and include a summary of the following: Patient demographics Baseline disease characteristics

Other patient characteristics will be summarized as deemed appropriate.

### 12.4. Determination of sample size

A total of 88 AML patients with FLT3 activating mutation will be enrolled. There are two study arms (44 patients per arm). Patients will receive crenolanib with chemotherapy. Arm 1 is for the AML or high-risk MDS patients who are refractory or has relapsed after prior therapy. Patients will be treated with standard salvage chemotherapy combined with crenolanib. Arm 2 is for the AML or high-risk MDS. Patients will receive azacitidine combined with crenolanib. For each arm, there will be 44 patients: in phase I, with 3 dose levels and Rolling-6 design, a maximum of 18 patients will be needed. With the 6 patients in the MTD dose enrolled in the following phase II part, for each arm, there will be 32 patients in total for phase II. In phase II, the primary endpoint is the response rate (CR+CRi+PR) after one or two cycles of treatment. The historical data suggested the response rate is 10%. With the assumption that the improved response rate to be 25%, it is estimated that a total of 32 evaluable patients

including the 6 patients from phase I will yield 79% power at a significance level of 10% based on chi-square test (nQuery software version 7.0).

### 12.5. Concomitant Therapy

Concomitant medication will be reported overall as well as summarized in a frequency table using the terms recorded on the CRF. If warranted, an attempt may be made to determine how concomitant medications are related to observed study outcomes.

### 12.6. Treatment Compliance

Treatment compliance information will be collected through pill counts at each tumor assessment visit and also by analyzing patient diaries where patients will record their daily drug intake. The estimate of percent compliance will be given by:

The number of tablets taken will be determined by counting the number of tablets returned at each visit and subtracting that number from the number of tablets dispensed. The number of tablets expected to be taken will be determined by the assigned dose and taking into account any prescribed dose reductions and omissions.

No minimal level of compliance will be defined for patient inclusion in efficacy analyses. An exploratory analysis of compliance may be performed by regressing percent compliance on selected efficacy endpoints. If significant results are indicated, analysis may be performed to determine the level of compliance that best delineates each endpoint.

### 12.7. Criteria for End of Study

This study will be considered complete following the data cut-off date for the final analysis. Documentation of the data cut-off will be included in the master study file.

After the final analysis, if patients are continuing to benefit from study treatment, they will be allowed to continue receiving study treatment. If patients continue on crenolanib beyond study closure, safety data must be collected. If further data are collected that are not included as part of the final locked database, the post hoc data will eventually be combined with the locked database and stored in a data library separate from the locked database.

### 13. DATA QUALITY MANAGEMENT

### 13.1. Data Quality Assurance

The quality of data will be ensured by the following:

- · Creating, implementing, and upholding standard operating procedures (SOPs) for trial execution
- · A quality scientific and medical design of the protocol: Changes to the protocol will be made only when protocol amendments have been signed by the principal investigator and approved by the sponsor and the IRB of the study center.

- · Clinical investigator and site pre-assessment and selection
- · Regulatory agency and ethics committee approval
- · Developing and providing appropriate informed consent (language, transparency of benefits and risks) and obtaining ethics committee approval of the informed consent process
- · Investigator meetings and training: Biweekly teleconferences with personnel at the study site will be set up to exchange key trial information and updates.
- · Adequate recording and reporting of data: A robust electronic data capture system (MERGE eClinical OS) is being implemented. This will ensure timely capture and verification of safety information. All patient data (including source data) generated in connection with this study will be kept in the archives for at least 15 years after the study has been completed. All data will be available for inspection by company representatives of the Medical Department and by regulatory authorities.
- · Periodic monitoring and audits: Sponsor will perform periodic on-site visits by monitors monthly for the duration of the study. Significant findings identified as a result of monitoring will be escalated for review by the sponsor, which may then be managed as a suspected significant deviation. Risk assessments and evaluations are then conducted. Remedial actions may include notifying regulatory authorities and ethics committees of any significant regulatory and/or GCP requirements.

